1.0 STUDY SYNOPSIS

Title of Study: An Open Label, Pilot Study Evaluating the Efficacy and Safety of the Use of Nasal Carbon Dioxide for the Treatment of Cluster Headache

Sponsor: [name]
Clinvest Research LLC
[name]
[name]
[contact]

Indication: For the treatment of cluster headaches in adults.

Primary Objectives: To evaluate the safety and efficacy of nasal CO₂ for the treatment of cluster headache.

Study Design:

This is an open label, investigator-sponsored, pilot study. Subjects agreeing to participate in the study and meeting the eligibility criteria assessed at the screening visit will be enrolled in the study. The length of time between screening and treatment will last between 0 days to a maximum of 12 weeks. Subjects who enter the screening phase during a cluster headache episode and meet the study eligibility criteria can immediately enter the treatment phase and may opt to treat their cluster headache episode in the clinic. Subjects who are not in a cluster headache episode, who meet initial screening eligibility criteria, can remain in the screening phase for up to 12 weeks until their next cluster episode begins. Upon initiation of a cluster headache episode, subjects will enter the treatment period. Subjects will be trained on the proper use of the hand-held dispenser containing CO₂ calibrated to deliver 0.5 standard liters per minute (SLPM). This dispenser will be provided for use in the clinic or home. Subjects will be instructed to use the nasal CO₂ dispenser, 10 seconds/nostril, as needed up to 6 times to treat one attack. Each dose must be separated by 3-5 minutes. Subjects should treat only one attack in a 24-hour period. Subjects may treat up to three cluster headache attacks during the treatment phase of this study. One hour after the first dose, subjects can choose to treat with investigator-approved rescue medication. Subjects will be asked to complete an online diary after the completion of the dosing. Diary assessments will collect pain severity (0=none, 1=mild, 2=moderate, 3=severe), symptoms (such as tearing, nasal congestion, and running nose), nasal CO₂ usage, acute medication usage, satisfaction of treatment, number of cluster attacks, and unusual symptoms. Subjects will be contacted by phone within 3 days of the first use of the nasal CO₂ dispenser to assess adverse events (AEs) and medication usage. A total of 25 subjects will enter the treatment period and be instructed to treat up to 3 cluster headaches with nasal CO₂. Within 7 days of treating their last cluster headache episode, subjects will return for an end of study visit.

Number of Subjects:	Up to 25 subjects enrolled and treating up to 3 cluster headaches in one cluster headache period.
Study Population:	
Subjects must meet all of the following inclusion criteria to be considered eligible for study entry:
 
1. Male and female, 18 years of age and older.2. History of cluster headache, as defined by International Classification of Headache Disorders (ICHD), third edition, beta version guidelines (ICHD-3 beta, Cephalgia 2013).3. Stable on concomitant medications, excluding those for the treatment of cluster headache, for at least 60 days prior to enrollment. 
Note: Subjects are allowed to use their usual standard of care for the preventative treatment for their cluster headache. Acute/abortive medications maybe used 60 or more minutes after the initial dose, limited to the following: triptans; high-flow oxygen.
 
4. If female and of childbearing potential, have a negative urine pregnancy test at the time of Screening.
a. To not be considered childbearing potential a subject must be surgically sterile, have had a hysterectomy or tubal ligation, post-menopausal for at least 1 year, or otherwise incapable of pregnancy.5. Capable of completing online headache diary with access to internet.6. Able to provide written Informed Consent.

Study Population (Cont'd): Subjects must not meet any of the following **exclusion criteria** to be considered eligible for study entry:

1. Recent nasal/midface trauma (< 3 months)
2. Recent nasal/sinus surgery (< 3 months).
3. Severe respiratory distress in the last 6 months.
4. Neoplasm such as Angiofibroma, sinus tumor, granuloma.
5. Nasal congestion present more than 10 days with fever (temperature \geq 100.4 °F) and nasal mucous is an abnormal color.
6. Surgery to treat cluster headache.
7. History of aneurysm, intracranial hemorrhage, brain tumors or significant head trauma.
8. Structural intracranial or cervical vascular lesions that may potentially cause headache attacks.
9. Other significant pain problems (including cancer pain, fibromyalgia, and trigeminal neuralgia) that might confound the study assessments in the investigator opinion.
10. Psychiatric disorder, which in the opinion of the Investigator, may interfere with the study.
11. Pregnant, actively trying to become pregnant, or breastfeeding, and/or is unwilling to use an accepted form of birth control.
12. Skin around and inside the nasal passage that is dry, cracked, oozing, or bleeding.
13. Recurrent nose bleeds, which in the opinion of the Investigator, may interfere with the study.
14. Is participating in any other therapeutic clinical investigation or has participated in a clinical trial and received treatment in the preceding 30 days.

Investigational Product:	0.17 L CO ₂ delivered through two 10 second administrations in each nostril, up to 6 times, to treat one attack (total of 1.0 L CO ₂). Subjects may treat up to three cluster headache attacks during the treatment phase of this study (total of 3.0 L CO ₂).
Efficacy Evaluation:	Primary Endpoints: Greatest change from pre-treatment headache pain intensity to post treatment at any time point within 30 minutes of Nasal CO ₂ administration.
	Secondary Endpoints: 
• Percentage of subjects experiencing headache pain freedom at 5-60 minutes within the treated attack• Percentage of subjects with headache relief at 5-60 minutes within the treated attack• Rescue medication usage for treated attack• Subject satisfaction• Cluster recurrence
Safety Evaluation:	Safety assessments will include: 
• Monitoring adverse events (AEs)• Concomitant medications
Statistical Methods:	Descriptive statistics will establish baseline characteristics and adverse event frequency. Data for each of the primary and secondary outcome measures will be statistically analyzed for within group changes via a 2-tailed repeated measures ANOVA and or independent or dependent t-tests as appropriate. All ANOVAs will be followed by univariate post-hoc tests.

Protocol 15-001CA
Nasal CO₂

Schedule of Events:

Study Procedures	Screening	Treatment	End of Study Visit¹
Informed Consent	X		
Eligibility	X		
Medical History/ Medications / Demographics	X		
Physical Examination with Neurological and Nasal Mucosal Exam	X		X
Vital Signs	X		X
Urine Pregnancy Test	X		X
Subject Training	X		
Subject eDiary, AE/ConMed diary, and Questionnaire Instruction	X		
Investigational Product Dispensation	X	X ²	
Accountability of Investigational Product and Study Supplies	X		X
Diary Completion		X	
Adverse Event Assessment		X	X
Concomitant Medications Assessment	X	X	X
Telephone Contact		X ³	X
eSource Document and eCRF Completion	X		X

¹ The End of Study Visit should occur within 7 days after the subject treats up to his/her third headache or within 7 days after the completion of the 84-day treatment period, whichever occurs first.

² Subjects will return to the clinic at 4 and 8 weeks after Screening Visit as necessary for a replacement dispenser.

³ Subjects will be contacted by telephone within 3 days of treating their 1st attack to answer any questions, assess if there are any problems with compliance or any concerning AEs.

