5.3 Duration

Once enrolled, each subject's participation in the trial may last up to 84 days (12 weeks) or once the subject treats up to 3 cluster headache attacks with the nasal CO₂ dispenser, whichever occurs first. There will be two scheduled clinic visits, Screening and End of Study Visit. The subject may return to the clinic 4 weeks and 8 weeks after the screening visit as necessary for a replacement dispenser. The End of Study Visit should occur within 7 days after the subject treats his/her last cluster headache attack or within 7 days after the completion of the 84-day treatment period, whichever occurs first. If a subject has not treated any cluster headaches during the 12 weeks treatment phase they can be allowed to continue in the study for an additional 12 weeks at the discretion of the Investigator.

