6.0 SELECTION AND WITHDRAWAL OF SUBJECTS

6.1 Inclusion Criteria

Subjects must meet all of the following inclusion criteria to be considered eligible for study entry:

- Male or female, 18 years of age and older.
- History of cluster headache, as defined by International Classification of Headache Disorders (ICHD), third edition, beta version guidelines (ICHD-3 beta, Cephalgia 2013).
- Stable on concomitant medications, excluding those for the treatment of cluster headache, for at least 60 days prior to enrollment.

Note: Subjects are allowed to use their usual standard of care for the preventative treatment for their cluster headache. Acute/abortive medications maybe used 60 or more minutes after the initial dose, limited to the following: triptans; high-flow oxygen.

- If female and of childbearing potential, have a negative urine pregnancy test at the time of Screening.
 - To not be considered childbearing potential a subject must be surgically sterile, have had a hysterectomy or tubal ligation, post-menopausal for at least 1 year, or otherwise incapable of pregnancy.
- Capable of completing online headache diary with access to internet.
- Able to provide written Informed Consent.

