6.2 Exclusion Criteria

Subjects must not meet any of the following exclusion criteria to be considered eligible for study entry:

- Recent nasal/midface trauma (< 3 months).
- Recent nasal/sinus surgery (< 3 months).
- Severe respiratory distress in the last 6 months.
- Neoplasm such as Angiofibroma, sinus tumor, granuloma.

Protocol 15-001CA
Nasal CO₂

- Nasal congestion present more than 10 days with fever (temperature ≥ 100.4 °F) and nasal mucous is an abnormal color.
- Surgery to treat cluster headache.
- History of aneurysm, intracranial hemorrhage, brain tumors or significant head trauma.
- Structural intracranial or cervical vascular lesions that may potentially cause headache attacks.
- Other significant pain problem (including cancer pain, fibromyalgia and trigeminal neuralgia) which in the opinion of the clinician, may interfere with the study.
- Psychiatric disorder which in the opinion of the Investigator may interfere with the study.
- Pregnant, actively trying to become pregnant, or breastfeeding, and/or is unwilling to use an accepted form of birth control.
 - Acceptable forms include: complete abstinence from intercourse from 2 weeks prior to administration of study drug, throughout the study, and for 7 days after completion or premature discontinuation from the study; sterilization of male partner when in a monogamous relationship; intrauterine device or implant with published data showing lowest expected failure rate is less than 1% per year; double barrier method (i.e., 2 physical barriers OR 1 physical barrier plus spermicide) for a least 1 month prior to Screening Visit and throughout study; or hormonal contraceptives for at least 3 months prior to Screening Visit and throughout study.
- Skin around and inside the nasal passage that is dry, cracked, oozing, or bleeding.
- Recurrent nose bleeds which in the opinion of the Investigator, may interfere with the study.
- Is participating in any other therapeutic clinical investigation or has participated in a clinical trial and received treatment in the preceding 30 days

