8.1.2 Medical History, Medications and Demographics

Subjects will be asked about their medical history and any medication and supplements they are currently taking or have taken within 30 days of the Screening Visit. Subjects will also be asked about their cluster headache history (e.g., age of diagnosis, typical associated symptoms, cluster headache pattern, etc.) and the pharmacotherapy and/or alternative treatment (e.g., homeopathy, natural health products, etc.) they have taken for their cluster headaches. In addition, the subject's demographic information (age, gender, race, and ethnicity) will be collected.

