8.1.6 Urine Pregnancy Test

Female subjects of childbearing potential will be given a urine pregnancy test at the Screening Visit and at the End of Study Visit. Subjects with a positive urine pregnancy test will be excluded or withdrawn from the study.

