8.1.12 Concomitant Medications / Procedures

Medications taken and procedures performed, within 30 days prior to the Screening Visit will be recorded in the subject's eSource/eCRF. Medications taken after the Screening Visit and until the end of the subject's participation in the study (End of Study Visit) will be recorded by the subject in the eDiary. Any rescue medication taken will also be recorded in the subject's eDiary. At the End of Study Visit as well as at any unscheduled visits, subjects will be asked about the medications, procedures and/or alternative treatments (e.g., homeopathy, natural health products, etc.) they have taken since their previous visit. All medication and procedures including rescue medication recorded by the subject on the diary will be discussed and reviewed by the Investigator or an appropriate member of the study site personnel, recorded in the subject's eSource/eCRF.

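### Subjects who wait for an episode have no eligibility re-confirmation before their first dose, and the 30-day medication record is shorter than the 60-day stability criterion

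*Combined protocol and SAP*

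**What the plan says.** **When eligibility is judged.** The Synopsis (Study Design) and 5.0 enrol those "meeting the eligibility criteria assessed at the screening visit will be enrolled in the study". The Eligibility row of the Schedule of Events (Synopsis and 8.2) has one mark, under Screening. Product is dispensed at that visit.

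**Who waits.** A subject already in an episode can start treatment at once. Subjects not in an episode "who meet initial screening eligibility criteria, can remain in the screening phase for up to 12 weeks until their next cluster episode begins". Under 5.3, if no headache has been treated by the end of the 12 weeks, "they can be allowed to continue in the study for an additional 12 weeks at the discretion of the Investigator".

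**Examinations and tests.** The nasal mucosal examination (8.1.5) is done at Screening and End of Study only. The same holds for pregnancy testing in 8.1.6: "Female subjects of childbearing potential will be given a urine pregnancy test at the Screening Visit and at the End of Study Visit".

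**Criteria and look-back.** Section 6.1 requires subjects to be "Stable on concomitant medications, excluding those for the treatment of cluster headache, for at least 60 days prior to enrollment". Section 6.2 has a 3-month limit for nasal or sinus surgery and for nasal or midface trauma, and a 3-month minimum for hormonal contraception. At Screening, 8.1.2 asks about medical history, with no stated window, and about "any medication and supplements they are currently taking or have taken within 30 days of the Screening Visit". Section 8.1.12 adds: "Medications taken and procedures performed, within 30 days prior to the Screening Visit will be recorded".

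**The concern.** Several 6.2 exclusions describe states that come and go: new injury to the nose or midface, new nasal or sinus surgery, cracked or bleeding nasal skin, congestion with fever, pregnancy, and treatment in another trial. A negative answer at Screening says little about them weeks later, when a waiting subject first applies gas to the nasal mucosa without staff present. If such a state has arisen, the first scheduled examination or pregnancy test that could show it is at End of Study, after as many as three treated attacks.

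The second matter is verification at Screening itself. A stability criterion that reaches back 60 days cannot be fully checked from a medication record that reaches back 30.

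At stake are a simple protection for subjects and the ability to document that a stated entry criterion was met. The point has no calculable effect on the efficacy analysis.

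**Working it through.** **1. The stated wait.** 12 weeks × 7 = 84 days. This agrees with the 84-day figure in 5.3, 6.3 and 7.1.1.

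**2. What lies between Screening and first dose for a waiting subject, and what each item covers.**
- Calls at about 4 and 8 weeks (8.1.13): questions, compliance, concerning AEs, replacement dispensers. Eligibility is not among them.
- Return to site at about 4 weeks (7.3): product exchange, compliance, retraining. Sections 5.3 and 7.1.1 and the Schedule of Events make the 4- and 8-week visits as-needed.
- Adverse events: 8.1.11 and 9.3.1 start collection of non-serious AEs after the first dose; SAEs are collected from enrolment. Section 8.1.11 also tells subjects to enter AEs in the eDiary from enrolment, and 8.1.3 records conditions reported after enrolment as AEs. A nosebleed or minor nasal injury during the wait is therefore in scope by one rule and out of scope by another.
- eDiary review: 5.6 gives it no timing; 8.1.11 places it at End of Study.
- Medication after Screening (8.1.12): entered continuously by the subject, reviewed at End of Study and unscheduled visits.
- 12-hour rule (7.2.2): concerns pain and headache treatments only.
- Pregnancy: 6.3 relies on the subject to tell the site; no test falls between Screening and End of Study.
- Scheduled call after treatment begins (8.1.13): within 3 days after the first treated attack, so after dosing.

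None of these is a pre-dose eligibility step.

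**3. Look-back at Screening.**
- Medication stability: 60 − 30 = 30 days lie outside the recorded window. Section 8.1.2 also covers drugs being taken now, whenever they were started. What escapes is a drug stopped entirely 31 to 60 days before Screening, plus dose changes in that period if nobody asks about them.
- Nasal or sinus procedures: taking 3 months as 89 to 92 days, the procedure record of 8.1.12 leaves 89 − 30 = 59 to 92 − 30 = 62 days uncovered. Medical history in 8.1.2 has no time limit, so surgery can be elicited there. Trauma is not touched by the 30-day limit at all.

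**4. Longest wait to first dose, by reading.**
- Synopsis and 5.0: at most 12 weeks, 84 days.
- 7.1.1: all treated attacks fall within 84 days of Screening.
- 6.3: no episode within 84 days of enrolment is a listed reason for removal.
- 5.3 with the extension, counted from Screening: (12 + 12) × 7 = 168 days.
- If a 12-week screening phase, the 84-day treatment period and the extension are read as consecutive: (12 + 12 + 12) × 7 = 252 days.

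The extension contradicts the Synopsis, 5.0 and 7.1.1. Its conflict with 6.3 is softer, because removal there is at the investigator's discretion.

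**The case against.** The strongest reply is that 6.1 and 6.2 set conditions for study entry, some of them expressly before enrolment or at Screening. The plan nowhere undertakes to show that subjects meet the criteria when they dose. That stands. A reader might infer that late-treating subjects are treated in breach of the criteria, or might measure how much of a 3-month or 6-month window falls after Screening. The documents do not support either step, because both move the reference date from entry to dosing.

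Other parts of the reply also stand:
- It would be wrong to say that every 3-month criterion has only a 30-day look-back, since medical history has no stated limit and Eligibility is a separate Screening procedure from the medication record.
- It would be wrong to say that half of the 60-day history is invisible, since current drugs are asked about whenever started.
- The word initial in the Synopsis may hint at a later check, but that is inference; the same paragraph places the assessment at Screening.
- A wait beyond 84 days cannot be taken as settled, because it rests on 5.3 alone and needs the investigator's agreement.
- The calls, the eDiary and the duty to report pregnancy could bring a problem to light.
- The protocol describes minimal systemic risk (3.4), and gives no evidence of harm from dosing after a change in nasal state or in early pregnancy.

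What the reply does not remove is that no contact before the first dose has the task of asking about the changeable exclusions, and that the required medication record is shorter than the criterion it should support.

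**Conclusion.** The point holds as a missing safeguard for waiting subjects and a documentation mismatch at Screening. It is not a violation of a stated criterion and does not invalidate the trial.

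Its size: up to 84 days between the only eligibility check and the first dose under the Synopsis, longer if the extension in 5.3 applies; and 30 of the 60 days of the stability period outside the recorded window, with the practical loss confined mainly to drugs stopped in those days. For surgery the mismatch is narrower, and for trauma it does not arise.

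Assumptions: 3 months is 89 to 92 days, and the number of waiting subjects is unknown. With up to 25 subjects it could lie anywhere from 0 to 25; those already in an episode who treat at once are unaffected.

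**What to change.** 1. **Look-back.** In 8.1.2 and 8.1.12, change 30 days to 60 days for medication and to 3 months for nasal and sinus procedures.
2. **Re-confirmation.** In the Treatment column of 8.2, add an eligibility re-confirmation mark for subjects not in an episode at Screening. Carry it out by re-asking the 6.2 items that are time-limited or can change, at the existing 4- and 8-week contacts and again when the subject enters the treatment period, before the first treated attack. Record the answers.
3. **Maximum wait.** Reconcile the Synopsis, 5.0, 5.3, 6.3 and 7.1.1, and state the date from which each period is counted.

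The cost is two look-back figures, a few more questions at contacts already planned, and a short call for each waiting subject. The call needs a small addition to 8.1.8 or 8.1.13, because the plan does not now say how a subject reports that an episode has begun. An occasional subject will be found ineligible before dosing; 6.3 already allows replacement of those who withdraw early. Re-asking about pregnancy will not find one that the subject does not know of; an additional test is not part of this recommendation.

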3.2 Cluster Headache

Cluster headache is a seriously debilitating disorder with 14 million individuals worldwide currently seeking treatment.² Characterized by recurrent bouts of excruciating unilateral pain with accompanying ipsilateral autonomic symptoms such as lacrimation, conjunctival erythema, nasal congestion, rhinorrhea, and occasionally a partial Horner's syndrome.³ Cluster headaches typically last between 15-180 minutes with 75% of attacks lasting less than 60 minutes if left untreated.⁴ They occur at a frequency of several times per day to several times a week with a cluster period typically lasting 8-12 weeks.

Cluster headaches are classified separately from migraine on the basis of more severe pain, more frequent attacks, shorter duration of attacks, different autonomic symptoms, and a different underlying pathophysiology. Interestingly, while migraine headaches are more commonly diagnosed in women, cluster headaches are up to 3 times more prevalent in men.^{3,4} Currently, the etiology cause of cluster headaches is not fully understood, however, there has been an increased interest in the role of the sphenopalatine ganglion (SPG) and trigeminal ganglion in cluster headache.⁶ Both of these ganglion innervate the sinuses and offer a potential therapeutic target for the treatment of cluster headache. Current standard of care treatments included both abortive and prophylactic medications; both with limited efficacy. During the onset of headache, many people respond to high flow oxygen and triptans have been shown to reduce severity and duration of attack, although do not demonstrate long-term prophylactic effects.

The social and economic burden of cluster headache is significant. Patients with chronic and active episodic cluster headache are severely impacted in non-economic and economic of their lives. A study by D'Amico et al found a 36% of cluster headache patients have lost their jobs and half the patients have reduced work time by at least 50%.⁷

Considering the inadequacy of current pharmacological therapy at considerable economic and social burden of this debilitating disorder, further research is warranted on alternative treatment options.

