5.2 Study Treatment

5.2.1 Dose Description

This is an open-label study so all eligible subjects will receive a nasal CO₂ hand-held dispenser. One dose will consist of a 10 second administration of nasal CO₂ to each nostril. Subjects will be instructed to use the nasal CO₂ dispenser, 10 sec/nostril, as needed up to 6 times to treat one attack. Each dose must be separated by 3-5 minutes. Subjects should treat only one attack during a 24-hour period with the investigational product. Subjects may treat up to three cluster headache attacks during the treatment phase of this study.

Subjects may receive up to a total of 1.0 L of CO₂ if they treat one attack with 6 doses. Subjects may receive a total of 3.0 L of CO₂ if they treat three headache attacks with 6 doses of CO₂ during this study.

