7.2.3 Rescue Medication

Subjects will be allowed to take rescue medication as prescribed by their physician if the headache(s) does/do not resolve or worsen(s) after completing the one-hour assessment. Subjects who take rescue medication will be asked to record the details of all medication taken through the 24-hour assessment (e.g., what medication they took, dose, when they took it, etc.) in the eDiary. The data recorded by the subjects in the diaries will be discussed at the End of Study Visit and all rescue medication taken by the subjects will be recorded on the subjects' appropriate eSource/eCRFs. If a subject uses rescue medication they are not allowed to treat the same headache again with Investigational Product.

Subjects who take rescue medication shall record the severity of their headache and associated symptoms at the 1 hour assessment.

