8.1.9 Subject Diary and Assessments

The primary and most of the secondary endpoint data will be collected from the electronic daily headache diary. Site personnel will be responsible for instructing subjects on the requirement for timely completion of the electronic diary. An email will be sent to subjects for completion of their headache diary containing a link to the diary. This link will take them to a survey queue

Protocol 15-001CA
Nasal CO₂

where all diaries will be available for completion. The diary for each headache should be completed during or immediately after each headache treated with nasal CO₂ and will document:

- Pain severity: (0=none, 1=mild, 2=moderate, 3=severe)
- Baseline pain severity
- Study medication usage
- Rescue medication usage
- Pain severity after initial treatment with nasal CO₂, symptoms at 5, 15, 30, and 60 minutes following treatment
- Headache resolution
- Unusual symptoms

All assessments must be completed as close as possible to the protocol-specified time of the assessment.

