10.0 STATISTICAL METHODS AND ANALYSIS

10.1 General Considerations

Tests will be conducted with a two-sided alpha = 0.05. Descriptive statistics and 95% confidence intervals will be presented with all analyses.

One interim analyses will be performed after 12 subjects have completed the study. All efficacy and safety analyses will be performed at the conclusion of the study.

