10.3.3 Secondary Efficacy Endpoints

The key secondary endpoints are:

Protocol 15-001CA
Nasal CO₂

- Percentage of subjects experiencing headache pain freedom at 5-60 minutes within the treated attack
- Percentage of subjects with headache relief at 5-60 minutes within the treated attack
- Rescue medication usage
- Subject satisfaction
- Cluster recurrence

This analysis will be assessed for the first headache treated with the investigational product.

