10.11 Deviation Reporting

Any significant deviations to the statistical analysis plan (Sections 10.1 through 10.11) will be addressed in the final report for this study.

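### The 60-minute pain-freedom test cannot separate a CO₂ effect from attacks ending on their own, because the protocol puts 75% of untreated attacks at under 60 minutes

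*Combined protocol and SAP*

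**What the plan says.** The only sentence in the combined protocol and SAP that names a test is in Section 1.0 (Statistical Methods). It says that each primary and secondary outcome will be "statistically analyzed for within group changes via a 2-tailed repeated measures ANOVA and or independent or dependent t-tests as appropriate". Section 10.1 adds: "Tests will be conducted with a two-sided alpha = 0.05. Descriptive statistics and 95% confidence intervals will be presented with all analyses". Sections 10.5 to 10.7 give the analysis population and say which attacks are analysed, but they name no test, null value or comparison rate. Section 10.11 treats Sections 10.1 to 10.11 as the statistical analysis plan.

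The endpoint is in Section 10.3.3: "Percentage of subjects experiencing headache pain freedom at 5-60 minutes within the treated attack". Section 8.1.9 has the diary record "symptoms at 5, 15, 30, and 60 minutes following treatment". There is no control arm (Section 5.2.1: "This is an open-label study so all eligible subjects will receive a nasal" CO₂ dispenser).

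Section 3.2 gives the natural course: "Cluster headaches typically last between 15-180 minutes with 75% of attacks lasting less than 60 minutes if left untreated". Under Section 7.2.3, rescue medication is open to subjects whose headache "does/do not resolve or worsen(s) after completing the one-hour assessment", so permitted rescue comes after the 60-minute score.

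**The concern.** A within-group test asks whether status has changed since before the dose. Subjects dose during an attack, so before the dose almost none should be pain-free. By 60 minutes, on the protocol's own figure, most attacks would have ended without treatment. The null hypothesis of no change is then false whether or not CO₂ works, and rejecting it shows only that attacks end.

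At stake is how one key secondary result is read. A small p-value at 60 minutes could be taken as a treatment effect, and nothing in the plan tells the reader to set the percentage against the natural course.

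**Working it through.** The plan gives no power or sample-size calculation, so there is no figure of its own to reproduce.

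**Inputs from the document**
- Untreated attacks over within 60 minutes: 75% (Section 3.2).
- Two-sided alpha: 0.05 (Section 10.1).
- N = 25 (Section 5.0) and N = 12 (Sections 10.1 and 10.3.2).

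**Assumptions**
- Pre-dose pain freedom is 0%. No minimum baseline pain is stated; 10% is tried below.
- The 75% applies from dosing. A lower rate of 50% is also tried.
- One attack per subject, with subjects independent.

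**Step 1: how many pain-free subjects give significance?** Let k of N subjects be pain-free at 60 minutes, each counting as a change from 0 to 1.

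Paired t-test: t = √[(N − 1)k/(N − k)].
- N = 25: k = 3 gives t = √(24 × 3/22) = 1.81, p = 0.083; k = 4 gives t = √(24 × 4/21) = 2.14, p = 0.043.
- N = 12: k = 3 gives t = √(11 × 3/9) = 1.91, p = 0.082; k = 4 gives t = √(11 × 4/8) = 2.35, p = 0.039.

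So 4 pain-free subjects suffice at either size. If all N are pain-free the variance is zero; this is counted as significant.

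Exact McNemar: p = 2 × 0.5^k. k = 5 gives 0.0625 and k = 6 gives 0.031, so 6 are needed.

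**Step 2: how often does an inert treatment pass?** The number pain-free is Binomial(N, r), where r is the natural 60-minute rate. The pass probability is P(X ≥ 4) for the t-test and P(X ≥ 6) for McNemar.

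| Natural rate r | N | t-test | McNemar |
|---|---|---|---|
| 75% (Section 3.2) | 25 | >99.99% | >99.99% |
| 75% (Section 3.2) | 12 | 99.96% | 98.6% |
| 50% (assumed) | 25 | 99.99% | 99.8% |
| 50% (assumed) | 12 | 92.7% | 61.3% |

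**Step 3: does the test separate active from inert?** If a drug raised the rate to an assumed 90%, McNemar would pass with probability above 99.99% at N = 25 and 99.99% at N = 12. At N = 25 this cannot be told apart from the inert case.

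**Step 4: sensitivity at r = 75%**
- *10% pain-free before dosing and staying so.* Changes are Binomial(N, 0.9 × 0.75 = 0.675). At N = 25 both tests pass with probability above 99.99%; at N = 12 the t-test passes 99.7% and McNemar 94.2%.
- *Onset versus dosing clock.* Assume durations spread evenly, 75% over 15–60 minutes and 25% over 60–180. Dosing 0 to 45 minutes after onset then gives an inert 60-minute rate of 0.69 to 0.78. McNemar passes above 99.99% at N = 25 and 95.2% to 99.3% at N = 12.
- *Change across the four post-dose times instead of from pre-dose.* Simulated repeated measures ANOVA (Greenhouse-Geisser), with assumed pain-free rates of 0, 0, 37 and 75%, passes above 99.99% at N = 25 and about 99.96% at N = 12. The course before 60 minutes is invented, so this shows only that the other reading does not remove the problem.

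**The case against.** **The test is partly constructed.** No passage says that 60-minute pain freedom is compared with pre-dose status. The synopsis sentence covers all outcomes at once and leaves the choice of test open, and the endpoint is a percentage, not a change score. This stands as a caveat: the reference is inferred. But the synopsis does plan to test each secondary outcome for within-group change, and the plan offers no other reference. Change across repeated attacks would escape the problem, but it would measure consistency, which is already an exploratory endpoint.

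**The 75% is a soft figure.** It is one background sentence about untreated attacks counted from onset. Trial subjects are timed from dosing, may take preventives and choose which attacks to treat. This stands, and it is why near-certainty is conditional: at an assumed 50%, McNemar at 12 subjects passes only 61.3%.

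**It is one time point of a secondary endpoint in an openly uncontrolled pilot.** This stands and limits the severity.

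Some stronger readings are tempting but not supported:
- *That the 60-minute data say nothing about CO₂.* Section 10.1 promises descriptive statistics and 95% intervals, and these remain informative. The fault lies in the p-value.
- *That the fault reaches the primary endpoint (within 30 minutes), earlier times or headache relief.* The document gives no natural-resolution rate for any of these.
- *That an inert treatment would often be significant while doing worse than untreated attacks.* Results from 4/25 to 13/25 are significant with an exact 95% interval wholly below 75% (4/25: 4.5–36.1%; 13/25: 31.3–72.2%). At a true 75%, though, such results have only about a 1.1% chance. They would point to harm or to the 75% not applying.
- *That early termination for efficacy would rest on this result.* Section 10.9 allows such termination but names no endpoint.

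**Conclusion.** The point holds for pain freedom at 60 minutes and no further. On the natural reading of the synopsis, the planned p-value cannot separate a CO₂ effect from natural resolution. This rests on a pre-dose pain-free rate near zero and on the Section 3.2 figure applying roughly from dosing. At the planned 25 subjects the conclusion is robust to the second assumption: even at a 40% natural rate, an inert treatment passes 99.8% (t-test) or 97.1% (McNemar). At 12 subjects it depends more on the rate and on the test chosen. Severity is minor to moderate: a stated analysis would mislead against the protocol's own figure, but on one time point of a secondary endpoint in a single-arm pilot.

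**What to change.** In the synopsis and Section 10.6:

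1. State that 60-minute pain freedom for the first treated attack will be reported as n/N with an exact (Clopper-Pearson) 95% confidence interval and no significance test against baseline. The same format may be used at 5, 15 and 30 minutes for consistency.
2. Show the result beside the protocol's 75% figure as context, not as a formal control. Note that the 75% counts untreated attacks from onset, whereas trial subjects are timed from dosing, may take preventives and choose which attacks to treat.
3. State that 60-minute pain freedom alone will not be taken as evidence of efficacy, and repeat this in Section 10.9.

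A formal test against 75% is not a workable substitute. With an upper tail of at most 0.025, 25 subjects would need 24 pain-free, with power of 27% at a true rate of 90%. At 12 subjects even 12/12 would not reject, since 0.75^12 = 0.032.

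The cost is wording only, with standard software and no new data. The price is that this endpoint loses its p-value and looks less favourable.
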